2.3.1 Attrition

For the sample size calculation, a maximum loss to follow-up of 10% per year (41% over 5 years) was assumed. The loss to follow-up rate encompasses all causes for subjects to be exited from the registry, including death, device explants, subject directed withdrawals, physician-directed withdrawals, and loss of contact with the subject.

Table 3: Primary Safety Endpoints Sample Sizes

	Primary Safety Endpoint 1	Primary Safety Endpoint 2
Sample Size of Evaluable Subjects	750 subjects	1000 subjects
Total Adjusted for Attrition	1271 subjects	1694 subjects

2.4 DATA ANALYSES

The analysis population for all primary endpoints in the registry will be the intention-to-treat (ITT) population. This population analysis will include all subjects who provide informed consent, met the enrollment criteria, and in whom a Protego lead was successfully implanted. Subjects enrolled prior to the Protego lead implant but not successfully implanted due to a Protego lead related complication (such as cardiac perforation caused by the Protego lead) will also be included in the ITT population.

Descriptive statistics will be used to present and summarize the data collected in the clinical registry. Frequency distributions and cross tabulations will be presented for discrete variables. Means, standard errors, and ranges will be presented for continuous variables.

Confidence intervals for the AE free-rate will also be estimated based on Kaplan-Meier estimates for freedom from adverse events together with the associated standard errors.

2.4.1 Endpoint Analysis

Primary safety endpoint 1 will be evaluated by performing an exact binomial test comparing the observed proportion (overall AE free-rate at 5 years) to 92.5%. Equivalently, the two-sided 95% lower confidence bound for the absolute difference between the overall AE free-rate and 92.5% must exceed zero.

The evaluation of primary safety endpoint 2 will be based on the exact, two-sided 95% confidence interval for the observed, individual AE rates at 5 years. The upper bound of these 95% confidence intervals must be less than 1%.

Secondary endpoints 1 and 2, which summarize pacing thresholds, sensing, impedance measurements and shock impedance measurements for the Protego lead, will be reported via standard measures, including means, standard deviations, medians, minimums, and maximums.

Secondary endpoint 3, which includes AEs that were excluded from primary safety endpoint 1, through 5 years post-implant will also be summarized as AE rates together with their associated, exact 95% confidence intervals.

2.4.2 Trend Analyses

The primary safety endpoints are evaluated at 5 years post-implant against pre-specified performance levels (92.5% for overall freedom from Protego lead-rated AEs, 1% for individual AE rates). To monitor the ongoing incidence of any potential AEs against the accumulating follow-up exposure post-implant, Kaplan-Meier survival curves will be prepared at the reporting intervals for these safety outcomes. Root causes for any failures, regardless of the incidence rates, will be investigated.

If the observed cumulative survival rates fall below the 5-year target values (92.5% of overall freedom from AEs, 99% for individual AEs) at any time during the registry, or are projected to fall below the target values, then BIOTRONIK will summarize the observed data and the results of its failure investigations, and report the findings to the FDA at or before the next scheduled status report. If at any time a single unanticipated adverse event or device failure, or combination of events, is believed to have implications regarding the safety of current or future subjects, then this will be reported to the FDA within the statutory timeframes.

2.4.3 Missing Data

All possible steps will be taken to minimize missing data in the registry. This includes but is not limited to monitoring of registry forms for completeness and supporting efforts to track and maintain contact with registry subjects during the follow-up period.

The reasons for any missing data in the registry will be documented. BIOTRONIK will examine both missing-data patterns, which describe which values are observed and which are missing, and the missing-data mechanisms, which concerns the relationship between missingness and the values of variables in the registry data set².

For evaluation of the long-term primary registry endpoints (safety endpoints 1 and 2), only subjects who achieve 5 years of follow-up or have experienced an adverse event prior to 5 years will be included in the final evaluation of the associated hypotheses. The secondary endpoint of other AEs at 5 years, excluded from the primary safety analyses, will be analyzed in similar manner. There will be no imputation for these missing adverse event outcomes.

For purposes of Kaplan-Meier survival analyses, described in Section 2.4.2, all AE data on enrolled subjects will be included with follow-up times censored at the time of withdrawal or last completed follow-up visit representing the time of the last known AE status.

² R.J.A. Little and D.B. Rubin, 2002, *Statistical Analysis with Missing Data*, 2nd edition, Wiley and Sons

Secondary endpoints, which include successful sensing and pacing, pacing thresholds, sensing and impedance measurements will be analyzed in two ways. First, all available results will be summarized by scheduled visit through the 5 years of registry follow-up. Secondly, a last value carried forward (LVCF) will be used to estimate the values at the final 5-year follow-up evaluation for subjects who withdraw prior to 5 years.

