2.3 SAMPLE SIZE ANALYSIS

The estimated sample sizes required to evaluate primary endpoints 1 and 2 are based on a superiority comparison of the overall Protego DF4 lead AE free-rate to 92.5% at 5 years, and a non-powered, superiority comparison for those individual lead-related AEs to 1% at 5 years. The sample size for primary safety endpoint 1 was calculated based on the following assumptions:

Assumptions for primary safety endpoint 1

- Study Design: nonrandomized registry
- Test basis: exact binomial test
- Type I error (alpha): 0.025 (one-sided for superiority)
- Statistical power: 80%
- Estimated AE-Free Rate at 5 years: 95.0% for Protego Leads
- Performance goal for AE-Free Rate at 5 years: 92.5%

For primary safety endpoint 1, a total of 750 evaluable Protego leads would be required to demonstrate superiority to an AE free-rate of 92.5% (see Table 3). Assuming a 10% loss to follow-up rate per year over 5 years of follow-up (average of 8.2% of original population per year), a total of 1271 ($=750/0.9^5$) subjects with an ICD lead would be required to be enrolled to evaluate primary safety endpoint 1.

Assumptions for primary safety endpoint 2

- Estimated individual AE rate at 5 years: 0.4%
- Allowable two-sided, upper 95% confidence bound: 1%

For primary safety endpoint 2, a total of 1000 evaluable subjects with Protego DF4 leads would be required to demonstrate a two-sided, upper 95% confidence bound of 1%, assuming an expected individual AE rate of 0.4% (see Table 3). Assuming a 10% loss to follow-up rate per year over 5 years of follow-up (average of 8.2% of original population per year), a total of 1694 ($=1000/0.9^5$) subjects would be required for evaluation of primary safety endpoint 2.

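### Section 2.4.3 drops event-free early exits but keeps every adverse event, so the tested 5-year AE rate is too high and endpoint 1 does not have its stated power

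*Combined protocol and SAP*

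**What the plan says.** Section 2.3 sizes endpoint 1 with "Test basis: exact binomial test", one-sided alpha 0.025, 80% power, an expected AE-free rate of 95.0% and a performance goal of 92.5%. It concludes that "a total of 750 evaluable Protego leads would be required to demonstrate superiority to an AE free-rate of 92.5" percent, and inflates this to 1271 enrolled by dividing by 0.9^5. Endpoint 2 sets the enrolment of 1694 (1000/0.9^5).

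Section 2.3.1 says "a maximum loss to follow-up of 10% per year (41% over 5 years) was assumed", and adds: "The loss to follow-up rate encompasses all causes for subjects to be exited from the registry, including death".

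Section 2.4.1 has endpoint 1 "evaluated by performing an exact binomial test comparing the observed proportion" with 92.5%. Section 2.4.3 then fixes who enters that proportion: "only subjects who achieve 5 years of follow-up or have experienced an adverse event prior to 5 years will be included", with no imputation.

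Kaplan-Meier appears beside this but decides neither hypothesis. Section 2.4: "Confidence intervals for the AE free-rate will also be estimated based on Kaplan-Meier estimates". Section 2.4.2 uses it, against the same targets, to trigger a report to the FDA: "If the observed cumulative survival rates fall below the 5-year target values (92.5% of overall freedom from AEs, 99% for individual AEs").

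**The concern.** The rule selects on the outcome. A subject with a lead-related AE in year 1 who then exits is counted. A subject who exits in year 1 without an AE is not. Events therefore come from everyone enrolled, and non-events only from 5-year completers. When exits are independent of AEs, the ratio overstates the 5-year AE rate, and by more when attrition is heavier or events come earlier.

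The sample size calculation ignores this. Dividing 750 by 0.9^5 is right only if the evaluable subjects have the population's 5% rate. A lead that performs exactly as assumed could then miss endpoint 1 because of the denominator. The same data could also clear 92.5% on the Section 2.4.2 curve and fail the formal test. This is an FDA-required registry, and its headline safety result would be the biased figure.

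The target is unsettled too. Section 2.1.1 describes a proportion of subjects, which suggests death as a competing event. Section 2.4.2 uses survival rates, which suggests deaths are censored. Section 10.3.1 gives a rule only for lead-related deaths. Section 10.2 uses total subjects as the denominator without defining it, and does not refer to Section 2.4.3.

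**Working it through.** **The plan's own figures.** With n = 750 and a null AE rate of 7.5%, the exact one-sided 0.025 test passes at 42 or fewer AEs (attained alpha 0.0247). At a true 5%, power is 80.1%. Also 750/0.9^5 = 1270.1 and 1000/0.9^5 = 1693.5. The stated 750, 80%, 1271 and 1694 all reproduce. An unbiased 1000 evaluable would have 88.9% power.

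**Inputs for the test as written.** From the plan: true 5-year AE rate 5%, attrition 10% per year, N = 1694. Assumed, because the documents are silent: exits independent of AEs, and three AE timings. These are constant hazard; early (half the cumulative hazard in the first 6 months, the rest even); and late (cumulative hazard proportional to time squared).

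**Constant hazard.**
- AE hazard h = −ln(0.95)/5 = 0.01026; exit hazard c = −ln(0.9) = 0.10536.
- AE observed before exit: a = h/(h+c) × (1 − exp(−5(h+c))) = 0.0887 × 0.4390 = 0.0390.
- Event-free at 5 years: b = 0.95 × 0.9^5 = 0.5610.
- Expected tested rate: a/(a+b) = 0.0390/0.5999 = 6.49%, not 5%.
- In counts: 1694 × 0.0390 ≈ 66 AEs among about 1016 tested subjects. With 1016 subjects the test allows at most 59.

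Power is the exact test averaged over the random number tested: M ~ Bin(N, a+b), and AEs given M ~ Bin(M, a/(a+b)).

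| 5% true rate, 10% yearly attrition | Constant | Early | Late |
|---|---|---|---|
| Tested AE rate | 6.5% | 7.2% | 6.0% |
| Power, 1694 enrolled | 21% | 5% | 46% |
| Power, 1271 enrolled | 16% | 5% | 35% |

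A separate simulation of the constant-hazard case at 1694 gave 20.9%.

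**Where the problem stops.** At 10% attrition, 80% power needs a true AE rate no higher than about 4.1% / 3.7% / 4.4% (constant / early / late). At a true 5%, it needs attrition no higher than about 4.4% / 3.4% / 5.7% per year. Under constant hazard at a true 5%, power is 52% at 7% attrition, 74% at 5% and 90% at 3%. At 10% attrition it is 83% for a true 4% and 99.9% for a true 3%.

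**False claims.** At a true 7.5%, the Section 2.4.3 test passes less than 0.02% of the time in all three timings.

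**Matched estimators (simulation, N = 1694, 10% attrition).**
- Deaths censored: Kaplan-Meier with a beta-product lower limit has 95% / 96% / 93% power at a true 5% and 2.0–2.2% type I error. On the same simulated data, Kaplan-Meier clears 92.5% while Section 2.4.3 fails in 74% / 92% / 48% of registries.
- Death competing, with deaths assumed to be 25%, 50%, 75% or 100% of exits (the documents give no split): cumulative incidence has 96–99% power at a crude 5% and 1.8–2.7% type I error (simulation SE about 0.2 points). Kaplan-Meier used for this target falls to 85 / 70 / 50 / 28% power under constant hazard, so the target has to be set first.
- With half of exits deaths, Section 2.4.3 reads a crude 5% as 7.4% / 7.7% / 7.1%, with power 3% / 1% / 7%. It fails under either target.

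**Section 10.2 read as all enrolled.** Under constant hazard and independent censoring, a true 5% would read as 3.9%, and a true 7.5% would pass about 75% of the time. That reading reverses the bias.

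**Endpoint 2** (stated as non-powered). At a true 0.4%, an unbiased 1000 passes 43% of the time (at most 3 events). Section 2.4.3 passes 25% / 19% / 32%, and Kaplan-Meier 59% / 62% / 55%.

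**The case against.** - **The error is conservative and visible.** It works against the device, Kaplan-Meier intervals will be reported, the FDA trigger uses them, and no action is tied to missing the test. This stands and limits the severity. It does not make the primary estimate right or the power statement true.
- **The 21% pairs maximum attrition with a 5% rate, and the predecessor did better.** The predecessor registry in Section 1.3.1 shows 2.5% (SE 1.0%) by Kaplan-Meier at day 1,465. Adding all its secondary lead AEs (33/1,999 = 1.65%) gives about 4.15%, where power under Section 2.4.3 is 75% / 46% / 91%. But day 1,465 is short of 5 years, and that primary endpoint was narrower. It left out dislodgement under 180 days and threshold or capture problems (22 + 7 of 1,999), which Section 10.3.1 excludes only within 30 days. The enrolment figures rest on 5% and 10%.
- **The timing range is assumed.** True, and it is not a bound: all AEs at implant gives 0.3% power, all at year 5 gives 89%. The direction holds in every case except that last extreme.
- **Some exits follow from AEs.** Explants are inside the 10%. Counting AE-related exits within it raises power only to about 30%.
- **The wording could cover any adverse event.** Early exits with some other AE would then stay in the denominator as non-events. If 10% / 20% / 30% of early exits without a primary AE had one (an assumption), power would be 42% / 64% / 82% under constant hazard. This is a strained reading of a sentence about the endpoint hypotheses, and at 10–20% the shortfall remains.
- **Comparing 21% with 80% mixes sample sizes.** Fair. Like for like, it is 89% to 21% at 1694 enrolled, or 80% to about 16% at 1271.

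**Conclusion.** The concern holds. As written, Section 2.4.3 tests a proportion that overstates the 5-year AE rate whenever event-free subjects exit early and exits are unrelated to AEs. The 80% power in Section 2.3 does not describe that test. At the plan's own 5% rate and 10% yearly attrition, with 1694 enrolled, the tested rate is about 6.5% (6.0–7.2% across the timings used) and power about 21% (5–46%). The direction is firm. The size depends on AE timing, attrition and the true rate, and it becomes unimportant at a true rate near 3% or attrition near 3% per year under constant hazard. The risk of a false claim of success is about zero. This should be fixed because the registry's formal conclusion would rest on the biased figure and could contradict the Kaplan-Meier result reported next to it. Endpoint 2 has the same defect but does not drive the severity.

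**What to change.** 1. **Sections 2.1.1 and 2.4.1:** state the target first. Deaths not related to the lead are either censored (lead AE-free survival) or a competing event (crude proportion of subjects).
2. **Section 2.4.1:** decide endpoints 1 and 2 on the matching 5-year estimate in the ITT population: Kaplan-Meier censored at exit for the first target, cumulative incidence with death competing for the second. Endpoint 1 is met if the two-sided 95% interval for the AE-free rate lies above 92.5%; endpoint 2 if it lies above 99% for that AE type. Name an interval suited to few events, for example beta-product for Kaplan-Meier, or Clopper-Pearson on the effective sample size for cumulative incidence. Both reduce to Clopper-Pearson without censoring. Report the other estimate as a sensitivity analysis.
3. **Section 2.4.3:** keep the completers-plus-events proportion only as a labelled sensitivity analysis, and do the same for secondary endpoint 3.
4. **Section 2.3 and Table 3:** replace the exact-binomial basis and restate power at 1694 enrolled for the chosen target. Under the assumptions above this is about 93–96% with deaths censored, or 96–99% for the crude target.
5. **Section 10.2:** keep the relatedness rule and refer to Section 2.4.1 for the denominator.

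The cost is a protocol amendment, presumably with FDA agreement because the registry is FDA-required. No new subjects or data are needed, since Section 3.3 already collects exits, death dates and device-relatedness of deaths. The drawback is that the interval is no longer plain exact binomial and assumes non-informative censoring. Withdrawals after explant may strain that assumption, which is why the sensitivity analyses stay.

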1.3.1 GALAXY Lead Registry: Clinical Experience with Linx ICD Lead

BIOTRONIK is currently conducting GALAXY, an after-market registry to confirm the long-term safety and reliability of the FDA approved Linx family of ICD leads. The GALAXY Registry is registered on clinicaltrials.gov, NCT00836589. This multi-center, prospective, non-randomized registry has been ongoing since enrollment began in January 2009 and has been closed to enrollment since November 2011. There were 1999 subjects enrolled in the registry, 196 of which were implanted with Linx^{smart} leads.

The sensing and pacing behavior was evaluated as well as the rate of lead related complications over the available follow-up period. The mean pacing threshold across all Linx and Linx^{smart} lead models was 0.63 ± 0.33 V. The mean sensing amplitude was 12.83 ± 5.43 mV. The mean lead impedance was 556.7 ± 124.8 ohms. There were 5 (2.55%) subjects who experienced a primary adverse event (AE) reported as related to the Linx^{smart} lead (Table 1) and 29 (1.45%) subjects who experienced a primary AE related to the Linx Lead Family.

Table 1: Linx Smart Lead Related Adverse Events

Adverse Event	Linx ^{smart} Leads (n=196)			All Linx Lead Models (N=1,999)		
	Subjects with AE, n	% Subjects with AEs	AEs, n	Subjects with AE, n	% Subjects with AEs	AEs, n
Primary Endpoint AEs						
Other ICD lead related: Lead oversensing or noise	3	1.53%	3	13	0.65%	13
Lead dislodgement > 180 days	1	0.51%	1	5	0.25%	5
Lead impedance out of range, High impedance, Potential conductor fracture	1	0.51%	1	5	0.25%	5
Lead impedance out of range, Low impedance, Potential insulation break	0	0.00%	0	5	0.25%	5
Lead undersensing or loss of sensing	0	0.00%	0	2	0.10%	2
Other ICD lead related: Tension pneumothorax	0	0.00%	0	1	0.05%	1
Total Primary Endpoint AEs	5	2.55%	5	29	1.45%	31
Secondary Endpoint AEs Related to the ICD Lead						
Lead dislodgement < 180 days	2	1.02%	2	22	1.10%	22
High pacing threshold, intermittent capture, no lead capture	0	0.00%	0	7	0.35%	7
Cardiac perforation with or without tamponade	0	0.00%	0	4	0.20%	5
Total Secondary Endpoint AEs	2	1.02%	2	33	1.65%	34
Total Primary or Secondary AEs	7	3.57%	7	60	3.00%	65

Figure 1 shows the calculated Kaplan-Meier actuarial graph demonstrating the freedom from all primary endpoint adverse events adjudicated by the Clinical Events Committee. Table 2 displays the associated case summary. A common, final follow-up date of November 4, 2013, is assumed for all active subjects.

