3.2 REGISTRY PROCEDURES

Patients will be enrolled \pm 30 days from implant of a BIOTRONIK DF4 compatible ICD or CRT-D device and Protego lead. BIOTRONIK Home Monitoring® should be activated in subjects who have a Home Monitoring® system. Home Monitoring® data can be utilized to assist in triage and diagnosis of lead-related adverse events between scheduled follow-ups. Subjects with a Home Monitoring® system will be seen for a routine in-office follow-up at least every 12 months and have the option to be followed by Home Monitoring® between routine in-office follow-ups at the intervening 6 month intervals. Subjects without a Home Monitoring® system will be seen for a routine in-office follow-up at least every 6 months.

Registry Procedure Visits:

- Enrollment
- Implant (collected retrospectively if before enrollment)
- Routine follow-up evaluations at 3 months post-implant and every 6 months post-implant for 5 years
- Interim evaluations for Protego lead-related events or system revisions

Table 4 summarizes the visit assessment schedule.

Table 4: Registry Visit Assessment Schedule

	Enrollment	Implant ¹	Routine Follow-up 3 Months and 6-60 Months (every 6 months ± 1 month) ²	Interim Evaluation (if applicable)
Informed Consent (enrollment)	X			
Demographics and Medical History	X			
Collect Implant Information	X ³	X ³		X
Device Evaluation		X	X	X
Adverse Event Assessment		X	X	X
Complete eCRF	X	X	X	X

¹Implant must be completed within 30 days of or no more than 30 days prior to enrollment/informed consent.

²Subjects using Home Monitoring® will be seen for a routine in-office follow-up at least every 12 months and may be followed by Home Monitoring® between routine in-office follow-ups at the intervening 6 month intervals. Subjects not using Home Monitoring® will be seen for a routine in-office follow-up at least every 6 months. If a registry visit is conducted via Home Monitoring® the site is required to call the subject on the date of the Home Monitoring® data collection and document the Investigators assessment of possible adverse events since the last registry visit.

³If implant was completed prior to enrollment, implant data is collected retrospectively at the enrollment visit. If the subject was enrolled prior to implant, implant data will be collected and entered at the time of the implant procedure.

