3.2.4.1 Device Programming

If Home Monitoring® evaluations will be used for routine follow-up visits, atrial and ventricular capture control should be programmed to “ON” or “ATM,” and Home Monitoring® activated. If atrial and ventricular capture control is not programmed “ON”/“ATM” or goes off automatically due to AF, high intrinsic rate, or other reason, the investigator will provide reasons in the EDC system.

3.2.5 **Unscheduled Interim Follow-ups**

Unscheduled interim follow-ups may occur anytime during the registry. Data collection is only required when a subject is seen for Protego lead-related reasons or due to a protocol defined adverse event. Other hospital or clinic visits that are unrelated to the device are not required to be entered into the EDC system.

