13.2 INVESTIGATOR REPORTS

Investigators are required to prepare and submit to BIOTRONIK the following complete, accurate, and timely reports on this registry when necessary:

- Notification of a subject death during the investigation
- Notification of the withdrawal of IRB/EC approval
- Annual progress reports prepared for the IRB/EC
- Notification of any deviations from the investigational plan
- Notification that an informed consent was not obtained from the subject

- Final summary report prepared for the IRB/EC
- Any other information upon the request of an IRB/EC, FDA, or BIOTRONIK

Table 5 outlines the responsibilities, including time constraints, for submitting the above reports.

Table 5: Investigator Reporting Responsibilities

Type of Report	Report to BIOTRONIK	Report to IRB/EC	Time Constraints of Notification
Subject Death During Investigation	Required	Required	BIOTRONIK as soon as possible and as required by reviewing IRB/EC
Adverse Event	Required	IRB/EC dependent	Within 10 calendar days after notification of the event
Unanticipated Adverse Device Effect	Required	Required	Within 10 working days after notification of the effect
Subject Withdrawal	Required		Within 5 working days
Withdrawal of IRB/EC Approval	Required		Within 5 working days
Progress Report	Required	Required	Submitted not less often than yearly
Significant Deviations from Investigational Plan	Required	Required	Within 5 working days after emergency to protect life or physical well-being of subject, otherwise prior approval by BIOTRONIK is required
Informed Consent Not Obtained	Required	Required	As soon as possible after discovery

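### Interim Kaplan-Meier curves count AEs after the last visit but drop event-free time over the same gap, which biases AE-free survival low when AEs are found and adjudicated between visits

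*Combined protocol and SAP*

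**What the plan says.** Section 2.4.2 makes the curves the registry's running safety check: "Kaplan-Meier survival curves will be prepared at the reporting intervals for these safety outcomes". If observed survival is below 92.5% overall, or below 99% for one AE type, at any time, the sponsor must summarise the data and report to the FDA. Table 6 sets progress reports at least yearly.

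Section 2.4.3 gives the rule for building the curves: "all AE data on enrolled subjects will be included with follow-up times censored at the time of withdrawal or last completed follow-up visit". It justifies this as the point at which AE status was last known.

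Other sections fix when information arrives:
- Section 3.2: "Routine follow-up evaluations at 3 months post-implant and every 6 months post-implant for 5 years".
- Section 3.2.5: "Unscheduled interim follow-ups may occur anytime during the registry", but "Data collection is only required when a subject is seen for Protego lead-related reasons or due to a protocol defined adverse event".
- Table 5: AE reports are due "Within 10 calendar days after notification of the event".
- Section 10.2: only events finally adjudicated as related count, in these curves too. Section 4.2 leaves adjudication timelines to the CEC charter.

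For the earlier GALAXY curve (Section 1.3.1): "A common, final follow-up date of November 4, 2013, is assumed for all active subjects".

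No section stops AEs at the last completed visit, defines a data cut-off for the curves, or sets a minimum number at risk.

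**The concern.** For a subject still in follow-up, the rule extends observation past the last visit only if an AE occurs. An AE two months after a visit enters the numerator. Subjects who were event-free over the same two months have already left the risk set. Censoring then depends on outcome, which Kaplan-Meier does not allow, and the estimate is pulled down.

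What is at stake is the monitoring signal. A lead performing as planned could be reported to the FDA as below target because of the censoring rule, and a true problem would be harder to tell from that artefact.

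**Working it through.** **1. The plan's own figures.** The documents give no figure for the interim curves, so the design figures are checked first. Exact binomial, n = 750, success at 708 or more AE-free: one-sided alpha 0.0247 at 92.5%, power 0.801 at 95%. Attrition: 750/0.9^5 = 1270.1, so 1271; 1000/0.9^5 = 1693.5, so 1694. All reproduce.

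**2. Inputs for the curves.** AE-free rate 95% at 5 years (Section 2.3), attrition 10% per year (Section 2.3.1), visits at 3, 6, 12, ... 60 months within 1 month (Section 3.2), accrual interpolated from Appendix B, and annual cuts. Constant hazards are an assumption:
- AE hazard = -ln(0.95)/60 = 0.000855 per month, or 0.0103 per year.
- Exit hazard = -ln(0.9)/12 = 0.00878 per month, with exits credited to the exit date.

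**3. Effect on the rate.** With AEs known at once, the apparent AE rate under the written rule is 0.0150 per person-year at month 24 after approval and 0.0129 at month 36. The implied share of time credited is 0.0103/0.0150 = 0.69 and 0.0103/0.0129 = 0.80. This agrees with direct counts of 70% and 80% of event-free time.

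**4. End-of-curve mean, no lag (4,000 simulated registries).**

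| Month after approval | As written | Active subjects credited to cut | AEs and time both end at last visit | True |
|---|---|---|---|---|
| 24 | 94.9% | 98.5% | 98.5% | 98.5% |
| 36 | 93.8% | 97.4% | 97.7% | 97.5% |
| 60 | 91.6% | 95.4% | 95.7% | 95.5% |
| 84 | 94.6% | 95.0% | 95.0% | 95.0% |
| 120 | 95.0% | 95.0% | 95.0% | 95.0% |

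**5. Chance that at least one annual curve is below 92.5% although the true rate is 95%.** Ranges are the spread over repeat simulations of 400 to 4,000 runs.

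| When AEs become countable | As written | Common cut-off |
|---|---|---|
| At once | 50-53% | 12-18% (same range if both end at last visit) |
| 10-day lag | 44% | 14% |
| 1-month lag | 37-45% | 9-10% |
| Half found only at visits | 27-40% | 7-10% |
| 3-month lag | 16-20% | 1-2% |

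With a 3-month lag, or with every AE found only at a visit, the mean bias of the written rule is near zero. For one AE type at the planned 0.4%, a false fall below 99% has probability 26% as written and 16% with a common cut-off (no lag). If the true 5-year AE rate is 2.5%, close to GALAXY, the chance of an overall curve below 92.5% is 17.5% as written and 5% with a common cut-off.

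**6. Where the effect sits.** The means in step 4 are pulled down by a few collapses in the tail. Median end-of-curve values with no lag are 0.987 as written against 0.991 with a common cut-off at month 24, and 0.961 against 0.970 at month 48: gaps of 0.4 and 0.9 points. At the month-60 cut, the gap is 0.1 points at 12 months of follow-up, 0.2 at 24 and 0.4 at 36. Ignoring events with fewer than 20 subjects at risk still leaves 31% against 9% in the first row of step 5, so the tail is not the whole effect.

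**7. The extreme case.** Suppose the cut falls just before 17 months after the first implant. Active event-free subjects are censored by about month 13 (the 12-month visit plus its window). If no one exited later, an AE at month 16 has a risk set of 1, and the estimate is multiplied by 1 - 1/1 = 0. Over all annual cuts, at least one curve reaches exactly 0% in 6.4% of registries as written, 0.2% with a common cut-off and 0.7% when both end at the last visit.

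**The case against.** The strongest reply is that the size rests on AEs being known at once. An event must be detected, reported and given a final related adjudication before it counts, and the adjudication timeline sits in a charter that is not among the documents. This stands: slow adjudication can offset the bias, and a reader who infers that every interim report understates survival goes further than the documents support. It does not rescue the rule, because the offset would be accidental and nothing in the plan provides for it.

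Second, stopping event-free time where AE status was last known is a recognised convention. That is true, but only if events stop there too.

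Third, a reader might infer that the GALAXY convention is the proven remedy. Section 1.3.1 describes that date only as assumed. Crediting everyone to the cut treats unascertained time as event-free. With a 3-month lag, the 24-month estimate at the month-48 cut is 0.983 against a true 0.980, while the written rule gives 0.980. For safety monitoring, erring high is arguably the worse direction.

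Fourth, the consequence is limited. The trigger is a report, due no later than the next status report, with no stopping rule. Section 2.4 also calls for Kaplan-Meier confidence intervals. This is fair, but the trigger is worded on the observed rate and not on a confidence bound.

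**Conclusion.** The point holds. As written, the interim curves treat events and event-free time in active subjects differently, and AE-free survival is biased low whenever AEs are found and adjudicated between visits. Under the plan's assumptions, with constant hazards and annual cuts, a lead with a true 95% rate has about an even chance of at least one false fall below 92.5% if there is no lag. That chance is 37-45% with a one-month lag and 27-40% if half of AEs surface only at visits. The mean bias is near zero with a three-month lag or if all AEs are found at visits. The direction follows from the text; the size is not fixed by the documents.

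Two stronger readings are not supported. A collapse to 0% is possible but rare (about 0.4-2% per annual cut through month 60), so it is not the main harm. The primary conclusions are also not at risk: the exact binomial tests in Section 2.4.1 do not use this rule, and the bias shrinks to 0.4 points by month 84 and to nothing by month 120. The change should still be made, because the curves feed the FDA trigger during the years when the bias is largest.

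**What to change.** In Section 2.4.3, end events and event-free time at the same point:

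- For each interim curve, count only qualifying AEs dated on or before the subject's own exit or last completed visit, and censor event-free subjects at that same point.
- Define that visit as a scheduled one (in-office, or Home Monitoring with its telephone call). An interim visit prompted by an AE would otherwise bring the asymmetry back. Likewise, count an AE that itself causes exit only once the next scheduled visit after it would have fallen due.
- List later AEs separately in every report, so that no safety signal is hidden.
- Add a sensitivity curve with a common data cut-off, as in GALAXY, set far enough before data lock to cover reporting and CEC adjudication. State that it errs high if AEs are found late.
- Print the number at risk, and pre-specify a minimum below which the curve is not read against 92.5% or 99%.

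The cost is a few sentences of SAP text and a small programming change, with no new data. The downside is that AEs after the last visit enter the curve one report later, which the separate listing covers. Adjudication lag can still leave the main curve slightly high, but less so than crediting everyone to the cut.
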